## 9. ENDPOINTS

The following endpoints will be analyzed, displayed graphically, and summarized through descriptive statistics. Endpoints will be reported among the analysis populations as well as among the pre-specified subgroups. Categorical endpoints may be collapsed where appropriate in case of data sparseness.

### 9.1. Primary Endpoint

The primary endpoint for this domain is the REMAP primary outcome of hospital free days at 90 days after the index date (HFD-90). The index date for HFD-90 outcome is defined as the date of the elective surgical encounter.

Hospital free days Score	Score
-1	Patient died during surgery or within the 90 days following their surgical intervention
0	No days out of the hospital in the 90 days following the surgical intervention
1-90	One to 90 days out of the hospital and alive in the 90 days following the surgical intervention

### 9.2. Secondary Endpoints

Secondary domain-specific outcome measures include information about EHR based alerts reported during the index elective surgical admission, perioperative outcomes, and surgical outcomes.

Specifically, they include:

- Perioperative outcomes (enrollment to postoperative 90 days)
  - Gastrointestinal intolerance (dichotomous; present/absent)
  - SAE as defined in Core Protocol (mild, moderate, severe, life threatening/disabling; adjudicated as related, possibly related, unrelated)

- Surgical outcomes
  - Index admission
    - Postoperative intensive care unit (ICU) admission (dichotomous; any admission/none)
    - ICU length of stay (LOS; continuous, days)
    - Hospital LOS (continuous, days)
    - Discharge disposition (categorical; Home, SNF/LTAC, Death/Hospice)
    - In-hospital mortality (dichotomous; yes/no)
  - 30-day outcomes
    - Organ failure free days (i.e., vasopressor exposure, hemodialysis, or mechanical ventilation; continuous, days)
    - Surgical site infection, as defined by NSQIP and the CDC (categorical)
    - Surgical site occurrence, as defined by Ventral Hernia Working Group (categorical)
  - 90-day outcomes
    - Reoperation/reintervention, both incidence and total number (dichotomous, time to event; any/none and continuous, number)
    - Readmission (dichotomous, time to event; any/none, days)
    - Venous thromboembolic events including deep vein thrombosis and pulmonary embolus after surgery (dichotomous, time to event; any/none, days)
    - Mortality (dichotomous, time to event; yes/no, days)

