## **6. INTERVENTIONS**

There is one active intervention and one control within this analysis plan:

- 1- Metformin
- 2- Placebo

Preoperative duration of study drug was pragmatically chosen based upon the time interval between the time of enrollment and scheduled operating room date including:

- 1- Short – 7-28 days
- 2- Medium – 29-90 days
- 3- Long – >90 days

Preoperative duration is not considered in the primary model but was considered in planned sensitivity analyses. Patients were randomly assigned,  $\sqrt{3}$ :1:1:1 to placebo and the 3 doses of metformin:

- 1- Placebo
- 2- Metformin 500mg ER
- 3- Metformin 1000mg ER
- 4- Metformin 1500mg ER

The dosing of and route of administration of metformin guidance included to take an oral dose once daily and complete all dispensed medication from the provided pill bottle.

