## **8. ANALYSIS POPULATIONS**

All participants who were randomized and underwent a surgical intervention within 365 days of randomization will be considered in our analysis population.

- SPRY intention to treat (ITT): This population consists of all patients enrolled and randomized to any treatment dose and duration. This population will only include those who underwent a surgical intervention at any time in the 365 days following randomization. All comparisons will be made based up the randomization table allocated treatment.
- SPRY per protocol analysis (PPA): This population consists of all patients enrolled and randomized who also completed randomization table allocated treatment and underwent a surgical intervention within 365 days of enrollment. Adherence to the protocol is determined by those who confirmed compliance with study drug at their 90-day postoperative evaluation with the study team. Compliance is defined by the verbal confirmation of study drug completion at the 90-day follow up timepoint.

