## 13.2. Analytic Approach for Secondary Endpoints

### *Primary Analysis*

The analysis of secondary endpoints will be conducted with Frequentist methods using unadjusted linear regression, logistic regression, and Cox models for continuous, dichotomous, and time-to-even secondary endpoints, respectively on both the ITT and PPA populations. Secondary endpoints are described in section 9.2 above. Treatment arms will be pooled across all durations and doses to form treated vs. placebo groups, with the placebo group used as the reference category in all analyses. There will be no adjustment for covariates, other than treatment arm.

The model structures will mimic the approach used in the frequentist analysis of the primary endpoint above. Specifically:

Linear regression:

$$y_i = \beta_0 + \beta_i * tx\_arm_i + \varepsilon_i;$$

Logistic regression:

$$y_i = \text{logit}(\beta_0 + \beta_i * tx\_arm_i + \varepsilon_i);$$

Cox Regression:

$$h(t|x_i) = h_0(t) * \exp(\beta_i * tx\_arm_i);$$

Where:

$y_i$  or  $h(t|x_i)$ : Secondary outcome of interest for subject  $i$

$\beta_0$  or  $h_0(t)$  = Coefficient for intercept or baseline hazard estimate

$\beta_i$  = Coefficient(s) for treatment(s) vs. placebo

$\varepsilon_i$  = Residual Error for Subject  $i$  (i.e. Subject-level random/residual error)

Statistical significance will be defined as an unadjusted  $p < 0.025$ . For all models, outputs will be reported using standard conventions and will include regression coefficients, standard deviations, confidence intervals, test statistics, and p-values, as relevant to each model. Model outputs will be reported both graphically and in tables, as described in sections 10 and 13.10.

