### *Sensitivity Analysis*

Secondary endpoints will be assessed for alternative definitions of treatment arm. Analyses will mirror the primary analysis of secondary endpoints, replacing the treatment arm with the following alternative definitions:

1. Metformin 1500mg ER vs. Metformin 1000mg ER vs. Metformin 500mg ER vs. Placebo (each pooled across duration) (Primary Approach)
2. Long Metformin (>90 days) vs. Medium Metformin (29-90 days) vs. Short Metformin (7-28 days) vs. Placebo (each pooled across the 3 doses of study drug)
3. Placebo vs. 500mg and 7-28 day duration vs. all other treatment combinations

Model structures will mirror the primary analysis of secondary endpoints and statistical significance

will again be defined as an unadjusted  $p < 0.025$ .

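### The by-duration sensitivity analysis of GI intolerance compares groups with unequal observation windows against one pooled placebo group, which can create an apparent duration effect when there is none

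*SAP*

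**What the plan says.** SAP 9.2 lists two outcomes under "Perioperative outcomes (enrollment to postoperative 90 days": "Gastrointestinal intolerance (dichotomous; present/absent", and "SAE as defined in Core Protocol (mild, moderate, severe, life threatening/disabling; adjudicated as related, possibly related, unrelated". Neither has a time-to-event form. The other outcomes in that section are tied to the index admission or to 30- or 90-day outcome periods.

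SAP 6 explains how the duration classes arise: "Preoperative duration of study drug was pragmatically chosen based upon the time interval between the time of enrollment and scheduled operating room date". The classes are 7-28, 29-90 and more than 90 days. SAP 8 limits the analysis population to patients who "underwent a surgical intervention at any time in the 365 days following randomization".

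SAP 13.2 analyses dichotomous secondary endpoints by logistic regression and states: "There will be no adjustment for covariates, other than treatment arm". Its sensitivity analysis keeps that model and changes the arms. Item 2 is "Long Metformin (>90 days) vs. Medium Metformin (29-90 days) vs. Short Metformin (7-28 days) vs. Placebo", and item 3 sets placebo against 500 mg with short duration against all other combinations. In both items placebo is one group pooled over durations.

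**The concern.** The variable that defines the groups is also the first part of the observation window. A patient in the long class is watched for at least 63 days more than one in the short class (181 minus 118). At equal prognosis, the chance of at least one event cannot fall as the window lengthens. The pooled placebo group mixes all three window lengths, so it sits between the short and long metformin groups even if the drug does nothing. Item 3 singles out the shortest window by definition.

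SAP 4 gives poor tolerance of study drug as one reason for stopping the trial, so readers will look for tolerability by exposure. These results would be tested at an unadjusted 0.025 and shown in forest plots. An artefact of window length could be read as toxicity that rises with duration, or as a safe short/low-dose regimen.

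**Working it through.** The documents state no window length, event rate or duration mix for these endpoints, so there is no plan figure to reproduce.

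**1. Windows.** Window = pre-operative interval (SAP 6; upper limit of 365 days from SAP 8) + 90 days (SAP 9.2).
- Short: 7+90 = 97 to 28+90 = 118 days.
- Medium: 29+90 = 119 to 90+90 = 180 days.
- Long: 91+90 = 181 to 365+90 = 455 days.

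The ranges do not overlap. The long/short ratio runs from 181/118 = 1.53 to 455/97 = 4.69. They are nominal: the class follows the scheduled surgery date, so a postponed operation lengthens the window, and death shortens it.

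**2. Odds ratio under no drug effect.** All inputs in this step except the class limits are assumptions.
- p90, the risk over the 90 post-operative days: 0.10 or 0.20; h = -ln(1 - p90)/90.
- r, the pre-operative daily hazard relative to the post-operative one: 0.05 to 1.
- pre, the pre-operative days: 17.5 (short midpoint), 59.5 (medium midpoint), 120 or 228 (long).
- Short/medium/long mix: 60/30/10 or 40/40/20.
- Risk in a class = 1 - exp(-h × (90 + r × pre)). Placebo risk is the mix-weighted average.

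One case in full: p90 = 0.20, r = 1, long pre = 228, mix 60/30/10.
- Risks: short 0.234, medium 0.310, long 0.545.
- Placebo: 0.6×0.2340 + 0.3×0.3097 + 0.1×0.5454 = 0.288.
- OR long = (0.5454/0.4546)/(0.2878/0.7122) = 2.97.
- OR short = (0.2340/0.7660)/(0.2878/0.7122) = 0.76.

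Range over all eight combinations at each r:

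| r | Short vs pooled placebo | Long vs pooled placebo |
|---|---|---|
| 1 | 0.63-0.82 | 1.52-2.97 |
| 0.25 | 0.85-0.94 | 1.17-1.52 |
| 0.10 | 0.93-0.97 | 1.07-1.21 |
| 0.05 | 0.965-0.987 | 1.04-1.11 |

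**3. Events early after the first dose.** Let H = -ln(1 - short risk), with short risk 0.10 or 0.30 over 107.5 days. Put a fraction f of H in the first 30 days and spread the rest evenly over the remaining 77.5 days, continuing at that rate to the end of a long window W of 181 or 225 days. Long risk = 1 - exp(-[fH + (1-f)H(W-30)/77.5]).
- f = 0.8: long vs short OR 1.20-1.38.
- f = 0.9: 1.10-1.19.
- All events within 97 days of the first dose: 1.00.

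**4. Would a person-time offset cure it?** Suppose all events are early and cumulative risk is equal in the short and long classes. The long/short rate ratio is then just the inverse ratio of windows: 107.5/210 = 0.51 or 107.5/318 = 0.34. The bias reverses and long duration looks safer.

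**5. Pooled contrast.** Dose or placebo was randomised and duration was not. Metformin and placebo therefore have the same expected mix of windows, and the main secondary-endpoint analysis is unaffected.

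**The case against.** A reader might infer that the plan must show more harm with longer duration. The documents do not support that. What is built in is a direction, not a size. Protocol 6.2.3 describes GI discomfort with metformin as self-limited, and the protocol summary lists GI distress that leads to stopping the drug. Both fit early events, for which the distortion is small. The larger odds ratios need a pre-operative daily hazard equal to that after major surgery. This objection stands and limits the claim on size.

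A reader might also infer that SAEs enter the same logistic model. SAP 9.2 defines SAE as a graded, adjudicated category and no model is named for it. The point reaches SAEs only if they are dichotomised and modelled, or tabulated by duration.

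Nor is it certain that by-duration tables are planned. SAP 11 lists tables by duration and dose, but SAP 13.2.1 restricts descriptive results for dichotomous, categorical and time-to-event secondary endpoints to treated versus untreated. The two sections conflict. Protocol 8.4.2 also ties the domain secondary outcomes to the index surgical procedure, which is a different window from SAP 9.2.

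The stakes are limited. The affected model is a sensitivity analysis, SAP 13.6 treats secondary endpoints as context, and SAP 11 bars modelling of groups with fewer than 10 subjects, which the long group may be. Duration was not randomised, so comparisons between durations are already open to confounding. Cumulative risk over a whole course is a legitimate quantity. The fault lies in setting it against a placebo group with a different mix of windows, and none of these limits removes that fault.

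**Conclusion.** The concern holds for GI intolerance in items 2 and 3 of the SAP 13.2 sensitivity analysis. Unequal windows and a pooled placebo comparator can make long metformin look worse, and short or short/low-dose metformin look safer, with no drug effect. The window lengths follow from the documents, but the size of the bias does not. Over the assumed risks, mixes and long intervals, the null odds ratio for long metformin against pooled placebo is about 1.04-1.11 when the pre-operative hazard is 5% of the post-operative one, and 1.5-3.0 when they are equal. It approaches 1 if events cluster soon after the first dose. The same reasoning covers SAEs only if they are dichotomised and modelled, and covers by-duration tables only if these are produced. Pooled metformin versus placebo is sound on this point. The importance is minor to moderate: worth correcting, but confined to a sensitivity analysis.

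**What to change.** - **Comparator.** In items 2 and 3 of the SAP 13.2 sensitivity analysis, compare each metformin duration group with placebo patients in the same pre-operative duration class. Stratify on the class, or add it as a covariate for all patients including placebo. For item 3, compare 500 mg/7-28 days with short-duration placebo, and the other combinations with placebo within class.
- **Between durations.** For any comparison of one duration with another, count events from surgery to postoperative day 90, which has the same length in every class. State that this remains a non-randomised comparison.
- **Offset.** Do not rely on a constant-rate person-time offset, because it reverses the bias if events are early.
- **Reconcile.** Settle SAP 11 against SAP 13.2.1 on by-duration tables, and Protocol 8.4.2 against SAP 9.2 on the observation window. State how SAEs will be modelled, if at all.

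The cost is SAP wording and a small programming change that needs event dates. Class-matched placebo groups are smaller, so precision falls, most of all in the long group. The post-operative window leaves out pre-operative events, including early ones after the first dose, so keep the full-window counts as a listing.

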Outcome measures	
Primary REMAP endpoint: hospital free days at day 90 after the surgical encounter
 
Secondary REMAP endpoints refer to Core Protocol
 
Secondary domain endpoints:
 
 1. Gastrointestinal distress causing discontinuation of the medication 2. Lactic acidosis 3. Hepatic dysfunction 
Serious Adverse Events (SAE) as defined in CORE protocol

TABLE OF CONTENTS

1. ABBREVIATIONS	6
2. PROTOCOL APPENDIX STRUCTURE	7
3. Metformin DOMAIN-SPECIFIC APPENDIX VERSION	7
3.1. Version History.....	7
4. Metformin DOMAIN GOVERNANCE.....	8
4.1. Domain Members	8
4.2. Contact Details.....	10
5. Metformin DOMAIN-SPECIFIC WORKING GROUP AUTHORIZATION	11
6. BACKGROUND AND RATIONALE	11
6.1. Domain Definition	11
6.2. Domain-specific Background	11
6.2.1. Guideline Recommended Use of Metformin and Potential Applications	12
6.2.2. Metformin Mechanisms of Action.....	13
6.2.3. Association of Metformin with Longevity in Small Clinical Trials	13
6.2.4. Metformin Safety Profile	13
7. DOMAIN OBJECTIVES	14
8. TRIAL DESIGN	15
8.1. Population.....	15
8.2. Eligibility Criteria	15
8.2.1. Inclusion Criteria for this Domain	15
8.2.2. Exclusion Criteria from this Domain	15
8.3. Interventions	16
8.3.1. Research Testing	16
8.3.2. Study Drug Intervention.....	16
8.3.3. Timing of Initiation of Intervention.....	17
8.3.4. Duration of Administration of Study Drug	17
8.3.5. Temporary Suspension of Study Drug.....	17
8.3.6. Suspension of Study Drug at the Direction of the Treating Clinician.....	17
8.3.7. Collection of Blood Samples	18
8.3.8. Collection of Samples for Microbiome Sub-study	18
8.3.9. Collection of questionnaires	19

8.3.10. Muscle Biopsy Sub-Study	21
8.4. Endpoints	23
8.4.1. Primary Endpoint	23
8.4.2. Secondary Endpoints.....	23
9. TRIAL CONDUCT	24
9.1. Domain-specific Data Collection	24
9.1.1. Clinical Data Collection	24
9.2. Criteria for Discontinuation	24
9.3. Blinding	24
9.3.1. Blinding	24
9.3.2. Unblinding.....	24
10. STATISTICAL CONSIDERATIONS.....	24
10.1. Domain-specific Stopping Rules.....	24
10.2. Strata.....	25
10.3. Timing of Revealing of Randomization Status	25
10.4. Interactions with Interventions in Other Domains	25
10.5. Post-trial Sub-groups.....	26
11. ETHICAL CONSIDERATIONS	26
11.1. Data Safety and Monitoring Board	26
11.2. Potential Domain-specific Adverse Events	26
11.3. Domain-specific Consent Issues.....	26
12. GOVERNANCE ISSUES	27
12.1. Funding of Domain.....	27

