8.4.2. Secondary Endpoints

All secondary endpoints as specified in the Core Protocol.

The domain-specific secondary outcome measures (occurring during the index elective surgical procedure), include:

- Hypoglycemia
- Gastrointestinal intolerance
- SAE as defined in Core Protocol
- 1 year mortality

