### **4. DESIGN CONSIDERATIONS**

SPRY investigates the effects of perioperative metformin on the primary outcome of 90-day HFD by pragmatically randomizing patients with different preoperative exposure durations to placebo or one of three doses of metformin. We planned to evaluate three preoperative exposure durations (short, 7-28 days; intermediate, 29-90 days; and long, 90 days) as well as three doses of metformin extended release (ER; 500mg, 1000mg, and 1500mg) among patients undergoing 14 surgical types (i.e., surgical strata). The primary Bayesian model, prespecified prior to patient enrollment, is a Bayesian ordinal logistic regression to estimate the effect of dose and duration of metformin on the distribution of HFD under placebo adjusting for expected differences given the surgical type/strata. Due to early discontinuation of the trial, 14 planned surgical types were consolidated into 6 surgical categories and three perioperative exposure durations were consolidated into one category for the primary Bayesian model.

In response to the COVID-19 pandemic, SPRY temporarily closed enrollment on 3/20/2020. On 8/17/2020, SPRY continued to enroll through in-person clinic-based screening and enrollment but

expanded to also complete virtual patient screening and enrollment. As a result, two enrollment strategies were utilized – in-person and virtual enrollment.

Prespecified adaptive randomization strategies for dose and duration dropping as well as thresholds for treatment efficacy, inferiority, futility, and equivalence were defined for interval analysis with 500 patients enrolled and for every additional 500 patients up to 2,500 followed for 90 days. The complete description of the *a priori* statistical analysis plan was completed prior to patient enrollment and previously published. However, the trial was discontinued prior to the first interval analysis due to low enrollment in the setting of COVID-19 and poor tolerance of perioperative study drug. As such, no interim results triggered response adaptive randomization. As previously planned, trial termination would result in public disclosure and a declaration of results.

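### SAP 9.2 omits four protocol-named secondary endpoints and replaces GI-related discontinuation with any GI intolerance, without explanation

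*SAP*

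**What the plan says.** The protocol lists domain secondary endpoints in two places.

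- The outcome row of the protocol summary gives "Gastrointestinal distress causing discontinuation of the medication 2. Lactic acidosis 3. Hepatic dysfunction", with SAEs alongside.
- Protocol 8.4.2 adopts all Core Protocol secondary endpoints and then gives a domain list: hypoglycemia, gastrointestinal intolerance, SAEs and "1 year mortality". It describes these outcomes as "occurring during the index elective surgical procedure".

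SAP 9.2 gives, from enrollment to postoperative day 90, "Gastrointestinal intolerance (dichotomous; present/absent" and SAEs classified by severity and relatedness. It then lists surgical outcomes, including in-hospital and 90-day mortality. Its opening sentence refers to alerts from the electronic health record during the index admission, but no alert appears in the list.

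SAP 12 says that early termination or non-adherence was recorded by coordinators and reported. It mentions neither a cause nor a comparison between arms. SAP 4 gives low enrollment during COVID-19 and "poor tolerance of perioperative study drug" as the reasons for stopping.

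**The concern.** A SAP written after a trial has closed should either carry forward each endpoint the protocol names or say why it has been retired. SAP 4 does this for the merging of surgical strata and preoperative durations. No such account is given for the endpoints.

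Three things are at stake.

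- **Tolerance.** Any GI intolerance, scored yes or no, cannot separate mild, self-limited symptoms from distress that ended treatment. The summary's endpoint measures the second, which is closer to the tolerance problem SAP 4 cites.
- **Per-protocol comparison.** SAP 13.1 runs the primary model in the per-protocol population as well as by intention to treat. SAP 8 defines that population by verbal confirmation of drug completion at day 90. If stopping for GI distress differs between arms, the per-protocol comparison is selected on a drug effect. Discontinuation by arm, with cause where known, is the information needed to judge that.
- **Named harms.** Protocol 6.2.4 raises hepatic damage and lactic acidosis as rare safety concerns, and protocol 11.2 lists lactic acidosis as a domain-specific harm. Under SAP 9.2 neither gets a named rate.

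**Working it through.** Neither document ties a sample size, power figure or event count to these endpoints, so the check compares the lists item by item.

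**Step 1: count the protocol items.** The summary gives 3 endpoints plus SAEs, which is 4. Section 8.4.2 gives 4. Only SAEs are in both, so there are 4 + 4 − 1 = 7 distinct items.

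**Step 2: trace each item.**

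| Item | Protocol summary | Protocol 8.4.2 | Collection list, protocol 9.1.1 | SAP 9.2 |
|---|---|---|---|---|
| SAEs | yes | yes | yes | kept |
| GI intolerance | no | yes | yes | kept |
| GI distress causing discontinuation | yes | no | no | altered to any GI intolerance |
| Lactic acidosis | yes | no | no | absent |
| Hepatic dysfunction | yes | no | no | absent |
| Hypoglycemia | no | yes | no | absent |
| One-year mortality | no | yes | no | absent; mortality ends at day 90 |

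The tally is 2 kept, 1 altered and 4 absent (2 + 1 + 4 = 7).

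**Step 3: look for the missing items elsewhere in the SAP.**

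- Sections 11 and 13.2.1 summarise endpoints but name none of the four.
- Section 12 covers early termination without cause or comparison.
- Section 13.2 takes its endpoints from Section 9.2, and its sensitivity analyses only redefine the treatment arms.

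An item missing from 9.2 therefore has no between-arm analysis anywhere in the SAP. That applies to 4 + 1 = 5 items.

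**Step 4: check what remains.** GI intolerance is dichotomous. It gets logistic regression for treated versus placebo, repeated by dose and by duration, and descriptive tables. SAEs are kept as an endpoint. Mortality to day 90 is modelled as dichotomous and time-to-event.

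**Step 5: check the protocol against itself.** The two lists share only SAEs. The window in 8.4.2, "occurring during the index elective surgical procedure", cannot contain "1 year mortality" from the same list. That endpoint also has no stated time origin.

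**The case against.** The best defence is that much of the gap starts in the protocol. The two lists conflict, and the SAP uses the GI term from 8.4.2, the section devoted to endpoints. The two outcomes in the collection list of protocol 9.1.1 are exactly the two domain items the SAP keeps. No lactate, liver, glucose or one-year item is listed there, and the blood samples in protocol 8.3.7 go to a biorepository for unspecified future use. This stands, and it may explain the omissions, but the SAP does not say so.

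The Core Protocol and the published analysis plan are not among the documents. The surgical outcomes in SAP 9.2 may come from the Core Protocol, so they cannot be called new. The SAE definition is there too, and SAP 9.2 grades SAEs from mild upward, so how many non-serious events SAE counts would miss is unknown. What stands is that SAE counts, as specified, give no named rate for any of the four absent items.

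Three stronger readings are tempting, and the documents do not support them.

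- **That safety and tolerance go unanalysed.** Step 4 shows that GI intolerance, SAEs and 90-day mortality are all analysed.
- **That this is selective reporting.** SAP 5 holds unblinding until the SAP is final, and nothing shows a choice driven by results by arm. It is an unexplained endpoint change.
- **That discontinuation is likely the most common drug effect.** The 30–60% in protocol 6.2.3 is self-limited GI discomfort in earlier trials, under other regimens. GI-related discontinuation is a subset of GI distress, and neither document gives a rate for it.

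**Conclusion.** The point holds as an unexplained mismatch between protocol and SAP. Four named secondary endpoints are absent. A fifth survives only as a broader GI variable plus early-termination records that state no cause. Following the SAP as written leaves all five without a comparison between arms, in a trial that stopped partly for poor tolerance and whose per-protocol population depends on drug completion.

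The primary endpoint and its model are unaffected. The loss is in the tolerance and safety record and in the reader's ability to interpret the per-protocol result. It cannot be expressed as a rate, because the documents give no event counts for these items.

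The conclusion assumes that SAP 9.2 is the full list of analysed secondary endpoints, as SAP 13.2 implies, and that the alerts it mentions without itemising do not cover the missing events. If they do, the remedy for those events is simply to list them.

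**What to change.** In SAP 9.2:

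1. Add study-drug discontinuation by arm, overall from the early-termination records in Section 12, and for GI distress where a cause was recorded. Report how often the cause is missing in each arm.
2. Add lactic acidosis, hepatic dysfunction and hypoglycemia from electronic health record data, enrollment to day 90, each with a written definition. Report by arm how many patients had the relevant test. Where events are too few to model, give counts and percentages by arm.
3. Add one-year mortality, with its time origin stated and completeness of vital status reported by arm.
4. Itemise the health-record alerts or delete the phrase.
5. Where data were never collected, retire the endpoint explicitly and give the reason.
6. Add a short note reconciling the two protocol lists and the window in 8.4.2. The trial is closed, so the SAP is the practical place for it.

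Items 1 and 4 to 6 need mainly wording and data already held. Items 2 and 3 need some extra abstraction, though SAP 11 already plans to use health-record data. The drawback is incomplete ascertainment: laboratory-based events depend on tests ordered in routine care, and one-year vital status may be missing for some patients. These results should be read with that in view.

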### *Frequentist Sensitivity Analyses*

In addition, sensitivity analyses will be conducted in which frequentist regression models are used in place of the Bayesian cumulative logistic regression and without borrowing across groups. For these analyses, we will assess HFD-90 by 4 definitions of treatment arms based on the intervention, on both the ITT and PPA populations:

1. Treated (any duration and/or dose combined to a single group) vs. placebo
2. Metformin 1500mg ER vs. Metformin 1000mg ER vs. Metformin 500mg ER vs. Placebo (each pooled across duration)
3. Long Metformin (>90 days) vs. Medium Metformin (29-90 days) vs. Short Metformin (7-28 days) vs. Placebo (each pooled across the 3 doses of study drug)
4. Placebo vs. 500mg and 7-28 day duration vs. all other treatment combinations

For each of these definitions, we will apply two approaches:

1. A frequentist proportional odds model for the cumulative odds of 90-day HFD being less than or equal to a cut point  $c$ , where  $c = -1, \dots, 89$ , as described in the primary Bayesian analysis above. The treatment effect will be estimated, adjusting for surgical strata and duration as covariates.
2. A Mann-Whitney U test with ties for differences in HFD-90 by treatment arm. Test statistics and p-values will be presented. We will report death as a dichotomous outcome (vs. no death) and, among survivors, HFD-90 as a continuous outcome, as outlined in Section 11.

In the logistic regression model, the model structure will be as follows:

$$y_i = \text{logit}(\beta_0 + \beta_i * \text{tx arm}_i + \varepsilon_i);$$

Where:

$y_i$ : Outcome (HFD-90 = 90 vs.  $\neq 90$ ) for subject i

$\beta_0$  = Coefficient for intercept (for odds of outcome for placebo (reference) group)

$\beta_i$  = Coefficient(s) for treatment(s) vs. placebo

$\varepsilon_i$  = Residual Error for Subject I (i.e. Subject-level random/residual error)

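### SAP 9.2 and 13.2 give no rule for death in length of stay, organ-failure-free days or readmission, so a mortality effect can distort these secondary results in a direction that depends on when deaths occur

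*SAP*

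**What the plan says.** SAP 9.2 defines the endpoints in question only by label and data type:

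- hospital stay: "Hospital LOS (continuous, days";
- ICU stay: "ICU length of stay (LOS; continuous, days";
- organ support over 30 days: "Organ failure free days (i.e., vasopressor exposure, hemodialysis, or mechanical ventilation; continuous, days";
- readmission over 90 days: "Readmission (dichotomous, time to event; any/none, days".

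None carries a rule for patients who die. SAP 13.2 analyses secondary endpoints with "unadjusted linear regression, logistic regression, and Cox models for continuous, dichotomous, and time-to-even secondary endpoints", comparing pooled metformin with placebo. SAP 10 and 11 prescribe Kaplan-Meier plots and percentiles for time-to-event endpoints. No competing-risk method is named.

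The primary endpoint is treated differently. SAP 9.1 gives the score -1, below every survivor, to this category: "Patient died during surgery or within the 90 days following their surgical intervention". The frequentist sensitivity analyses in SAP 13.1 add a second device, again for HFD-90 only: "We will report death as a dichotomous outcome (vs. no death) and, among survivors, HFD-90 as a continuous outcome".

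In-hospital mortality, 90-day mortality and a discharge disposition that includes death are separate secondary endpoints in SAP 9.2. They are not combined with stay, organ support or readmission.

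**The concern.** A day count has a clear direction only if every patient had the chance to accumulate days. A patient who dies in hospital on day 3 has a three-day stay and can never be readmitted. A linear model of days and an any/none logistic model read that as a good result on both endpoints. Any effect of metformin on mortality, in either direction, therefore feeds into these results, and the reader cannot separate it from an effect on recovery.

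The secondary endpoints are meant to give context to HFD-90 (SAP 13.6). If stay and readmission appear worse on metformin because more patients survived to accumulate them, that context misleads. The same holds in mirror image if metformin caused early deaths.

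Two other parts of the SAP do not help. The missing-data rule in 13.5 does not mention death; if a death were treated as missing, the patient would receive the dose-group median, a typical value. And the per-protocol population in SAP 8 requires verbal confirmation of drug completion at day 90. A patient who has died cannot give this, so on that wording the per-protocol analysis covers survivors only, while the ITT analysis keeps the deaths. The same endpoint then handles death differently in the two populations.

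**Working it through.** The plan states no event rate, expected stay or power for these endpoints, so there is no figure to reproduce. The check asks what the stated models return if metformin does nothing except turn some in-hospital deaths into survivors.

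**Formula.** Let p0 and p1 be mortality on placebo and metformin, D the endpoint value recorded for a death, S the value for a rescued patient, and m the mean in all other patients.

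- Placebo mean = (1 - p0)m + p0·D
- Metformin mean = (1 - p0)m + (p0 - p1)S + p1·D
- Difference (metformin minus placebo) = (p0 - p1)(S - D)

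**Inputs.** All are assumptions; none is in the documents.

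- Mortality 2% vs 1%, 4% vs 2%, 6% vs 3%, all in hospital.
- Base case: death on day 3 after three days of organ support; a rescued patient has five days of support (30 - 5 = 25 free days) and goes home on day 15.
- 40% of rescued patients are readmitted.

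| Endpoint and handling of death | S - D | 2% vs 1% | 4% vs 2% | 6% vs 3% |
|---|---|---|---|---|
| Hospital stay, death on day 3 | 15 - 3 = 12 | +0.12 d | +0.24 d | +0.36 d |
| Hospital stay, death and rescue both 20 d | 20 - 20 = 0 | 0 | 0 | 0 |
| Hospital stay, death at 30 d, rescue 15 d | 15 - 30 = -15 | -0.15 d | -0.30 d | -0.45 d |
| Any readmission | 40% - 0 | +0.4 points | +0.8 points | +1.2 points |
| Organ-failure-free days, days after death counted as free | 25 - 27 = -2 | -0.02 | -0.04 | -0.06 |
| Same, days after death not counted | 25 - 0 = 25 | +0.25 | +0.50 | +0.75 |
| Same, death scored -1 | 25 + 1 = 26 | +0.26 | +0.52 | +0.78 |

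The first three rows show that the sign for length of stay is set by the timing of deaths. The last three show that the sign for organ-failure-free days turns on a definition that the supplied text does not give.

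**Could it reach significance?** The trial stopped before its first interval analysis, planned at 500 enrolled, so 500 is taken as a ceiling. The allocation in SAP 6 gives a placebo share of √3/(√3 + 3) = 36.6%, or 183 vs 317. In 4,000 simulated trials per scenario, deaths occurred on day 2, rescued patients stayed 20 days, and other stays were lognormal (median 4, mean about 5 days). The arms were compared by t-test, which is equivalent to the unadjusted linear model.

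| Mortality | Stay declared longer on metformin (one-sided 0.025) | Same, death given 90 d | Stay declared shorter, death given 90 d |
|---|---|---|---|
| 2% vs 1% | 5% | 0.4% | 11% |
| 4% vs 2% | 13% | 0.2% | 19% |
| 8% vs 4% | 39% | 0.0% | 33% |

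The 90-day value is only a device to show what ranking death worst does. These rates describe the early-death case and are not a forecast for this trial.

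**The case against.** A reader might infer that these endpoints always point the wrong way when the drug saves lives. The documents do not support that. The length-of-stay bias is zero when deaths have the same stay as rescued patients, and it reverses when deaths follow longer stays. Nor does a death after discharge shorten the index stay.

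A reader might also infer that organ-failure-free days is reversed as specified. The SAP is silent rather than wrong here: it does not say that days after death count as free. Protocol 8.4.2 defers secondary endpoints to a Core Protocol, and SAP 4 refers to a previously published plan. Neither was supplied, and either may hold the definition.

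The criticism of readmission applies mainly to the any/none analysis. A Cox model that censors at death estimates a cause-specific hazard, which is a recognised quantity. Finally, mortality is reported beside these endpoints, HFD-90 already ranks death worst, and the shifts are fractions of a day.

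All of this stands as a limit on the claim. It does not remove the gap. Reporting mortality shows how many died but does not correct the other models. A bias whose sign depends on the unknown timing of deaths needs a stated rule. Kaplan-Meier curves with deaths censored still overstate the incidence of readmission and other non-fatal events.

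**Conclusion.** The concern holds for secondary endpoints only. Followed as written, the linear and logistic models count an early in-hospital death as a short stay with no readmission, and nothing in the supplied documents overrides this. With early deaths, a survival benefit can appear as longer stay and more readmission; with deaths after long stays, the length-of-stay distortion disappears or changes sign. For organ-failure-free days, the supportable statement is that the handling of death is undefined in the supplied documents, and that the sign can flip if days after death count as free.

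The size is small when mortality is low: +0.12 to +0.36 days of mean hospital stay over the base-case range, resting on assumed mortality, day-3 deaths and 15-day rescued stays. HFD-90 and the primary conclusion are unaffected. The point should be corrected, but it does not threaten the trial's main result.

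**What to change.** Add a death rule for each endpoint to SAP 9.2 and 13.2:

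1. **Organ-failure-free days:** score death by day 30 as -1 and analyse with the cumulative logistic model already used for HFD-90.
2. **Hospital and ICU stay:** analyse time to discharge alive with in-hospital death as a competing event, or rank death worst. Keep descriptive medians, shown beside mortality.
3. **Readmission:** start the clock at live discharge with death as a competing event, and label the Cox result as a cause-specific hazard. Because live discharge selects survivors, also report readmission or death by day 90 in all ITT patients, beside the any/none analysis.
4. **Plots:** use cumulative incidence instead of Kaplan-Meier for non-fatal time-to-event endpoints. Reoperation and venous thromboembolism have the same gap, since deaths censored in a Kaplan-Meier curve inflate their incidence too.

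SAP 5 ties unblinding to finalisation of the SAP. If unblinding has already taken place, report these as labelled sensitivity analyses.

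The cost is SAP wording and modest programming. No new data should be needed, because discharge disposition, length of stay and timed mortality and readmission are already endpoints. The drawback is that length of stay is no longer summarised as one difference in mean days.
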